10.3 GENERAL NOTES

Analyses of MAEs and other adverse events will be conducted at exact time points. Early events are defined as those occurring from the date of the procedure to 30 calendar days post-operatively. Late events are defined as those occurring from after 30 calendar days post-operatively (from day 31 forward). Events within six months and one year, respectively, are those occurring up to and including

*Steele R and Torrie J. Principles and Procedures of Statistics. 1960. McGraw-Hill, New York.

Confidential. This document and the information contained herein may not be reproduced, used or disclosed without written permission from Endologix, Inc.

180 days and 365 days following the procedure.

For categorical variables, summary statistics will include counts and proportions. Confidence limits for proportions will generally be given; for binary variables the confidence limits will be computed using the exact binomial distribution. Supportive multivariate analyses of stratified comparisons of categorical variables will be performed using appropriate logistic or Cox regression.

For continuous variables, summary statistics will include means, standard deviations, medians, and range. Groups will be compared using *t*-tests or analysis of variance, or Kruskal-Wallis tests will be used to compare more than two groups (such as trial sites). When multiple comparisons are performed after ANOVA, Scheffé's method will be used. The exact Wilcoxon test will be used to compare continuous variables where severe departures from normality are observed.

For ordinal variables, comparisons will be performed using the exact Wilcoxon rank-sum test. Unless otherwise specified, the exact form of each algorithm will be the default of SAS Version 9.1 or later. Some preliminary descriptive analyses may be done with other software tools to be specified.

10.4 BASELINE COMPARABILITY ANALYSIS

A set of important demographic or prognostic variables will be compared across study sites to determine homogeneity of sites in terms of baseline patient characteristics. Factors found to differ significantly by site will identify that variable or site as a possible covariate in subsequent analyses.

In the analysis of comparability of trial sites, it is anticipated that a small number of sites may have a patient enrollment that is too small to allow meaningful statistical analysis. To allow the inclusion of sites with this condition, small sites will be combined into one pseudo-site the size of which will not exceed the size of the largest trial site. It is not possible to determine the number of subjects below which this aggregation will occur until after enrollment is completed, but generally trial sites with four or fewer subjects may be combined.

10.5 POOLING

Data pooling incorporates two factors: combination of data across sites and the actual method of obtaining an estimate of the endpoint from combined data. Data will be combined from multiple study sites for the study analyses. The justification for this pooling is made on a clinical basis with three critical factors: The basis for pooling comes from: 1) The study sites must implement one common protocol; 2) The sponsor must ensure consistent application of study procedures and compliance with the protocol; and, 3) the study sites must use common data collection procedures.*

In order to determine if there is a similar response across the study sites for each response, the primary safety and effectiveness will be tested for homogeneity by extension of the Fisher's exact test (Fisher-Freeman-Halton).. If the P-value for study site is less than 0.15 for any response, differences between study site will be assumed to exist and the overall estimate of the proportion in the test subjects will be obtained by taking a weighted average of the proportions at each site with the weight being the inverse

*Meinert C. Clinical Trials: Design, Conduct, and Analysis. 1986; Oxford University Press. New York, NY

Confidential. This document and the information contained herein may not be reproduced, used or disclosed without written permission from Endologix, Inc.

of the variance of the proportion at that site.* The sum of these weighted proportions divided by the sum of the weights will be the overall estimate for the study. Both the safety and effectiveness measures will employ weighted proportions as the basis for the statistical test. The test of significance in these circumstances are fully described below in Sections 10.6 and 10.7.

If the heterogeneity P-value is less than 0.15, an analysis of the primary effectiveness endpoint by the Fleiss (1993) method will be done. The estimates obtained from this method provide a mechanism to test homogeneity and to adjust the value of the overall estimate if heterogeneity exists.

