10.6.3 Analysis Plan

All subjects who receive treatment will be included in the safety analysis.

A univariate test will be done with the exact binomial distribution to determine if the frequency of MAE in the study population is statistically significantly less than 0.56. The formula for this test is provided below.

$$P(X \leq x_t | 0.56) = \sum_{k=1}^{x_t} \binom{n_t}{k} 0.56^k 0.44^{n_t-k} < 0.025$$

Where x_t is the number of study subjects experiencing an MAE and n_t is the number of subjects in the study. If the above expression holds for the observed x_t , the null hypothesis will be rejected and the alternative hypothesis will be accepted.

If there is heterogeneity among the study sites in MAE response, the analysis will be done by the method of Fleiss (1993). The test statistic will be given by the following formula.

$$z = \frac{(\bar{p}_T - 0.56)}{SE(\bar{p}_T)}$$

Where the formula for the weighted estimate of the proportion is given by the following:

$$\bar{p}_T = \frac{\sum_k W_k p_{Tk}}{\sum_k W_k}$$

And the formula for the weight in site k is given by the following:

$$W_k = \left(\frac{1}{n_k} p_k (1 - p_k) \right)^{-1}$$

And the formula for the standard error is given by the following:

$$SE(\bar{p}_T) = \left(\sum_{k=1}^{m_T} W_{Tk} \right)^{-1/2}$$

If the z has a P-value less than a one-sided alpha of 0.025, the null hypothesis will be rejected and the alternative will be accepted.

To determine those factors that may be associated with MAE, a supportive covariate analyses will be performed by logistic regression to determine if there are differences in the rates among groups when adjusted for other factors in the study population only. Covariates for these analyses will be age, gender, ASA class, cardiac/coronary artery disease (a composite variable to include arrhythmia, CHF, prior MI, CABG/PCI, heart valve repair/replacement), histories of cancer, cerebrovascular accident, coagulopathy, COPD, diabetes, hypertension, liver disease, peripheral arterial occlusive disease, renal failure, smoking, maximum aneurysm diameter, and study site. The final model will be reduced by backward elimination until no covariate terms remain in the model with a P-value less than 0.05.

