10.7 PRIMARY EFFECTIVENESS ANALYSIS

10.7.1 Primary Effectiveness Hypothesis

The primary effectiveness hypothesis is that the Treatment Success rate at one year exceeds a performance goal of 80%. The hypothesis test will be evaluated using the exact binomial distribution as a one-tailed test, using significance level $\alpha=0.05$. Multivariable analyses will be used to assess predictors of success. The null and alternative hypothesis is presented below.

$$H_0: P \leq 0.80 \quad \text{vs.} \quad H_1: P > 0.80$$

Where P is the rate of Treatment Success as defined in §10.7.2.

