10.7.2 Sample Size

The primary trial effectiveness variable is the Treatment Success rate at one year post-operatively. Treatment Success is a composite of clinically-relevant outcomes, including procedural technical success and freedom from: aneurysm rupture; conversion to open repair; Type I endoleak at 12 months; Type III endoleak at 12 months; clinically significant migration; aneurysm sac enlargement; or secondary endovascular procedure up to 12 months for resolution of Type I or III endoleak, device occlusion, migration, aneurysm sac expansion and/or a device defect.

The sample size is obtained by using the exact binomial distribution using PASS 2008. A sample size of 132 subjects at one year in the study population will have 80% power against a null performance goal of 80% if the proportion of Treatment Success is 88% or higher. It is estimated that the rate of Treatment Success will be greater than 88%.

It is anticipated that the drop-out rate of the trial will be 12% or less. Because the larger of the two sample sizes after adjustment for loss to withdrawal is the one for effectiveness, a minimum

of $132/0.88 = 150$ subjects will need to be recruited for this study. Thus to allow for deviations from assumptions, 150 subjects will need to be recruited for this study.

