10.7.3 Analysis Plan

The primary effectiveness analysis will compare the Treatment Success rate as defined previously to a target rate of 80%. The null and alternative hypotheses are defined below.

$$H_0: P_t \leq 0.80$$

$$H_1: P_t > 0.80$$

Where P_t = the proportion of treated subjects who meet the Treatment Success definition. The observed proportion of subjects with Treatment Success at one year post-procedure will be tested with the exact binomial distribution under the null hypothesis given in the inequality above. The formula for this expression is presented below.

$$P(X > x_t | 0.80) = \sum_{k=x_t}^{n_t} \binom{n_t}{k} 0.80^k 0.20^{n_t-k} < 0.05$$

Where x_t is the number of successes at one year and n_t is the number evaluated. If the one-sided P-value is less than 0.05, the null hypothesis will be rejected and the study hypothesis will be demonstrated.

If the study site success proportions across study site are not homogeneous, then the method of Fleiss described above will be used in the Test arm only to obtain a weighted estimate of the proportion successful. The mean proportion is found the same way as the first equation above. The test statistic becomes a z-statistic with the following formula:

$$z = \frac{(\bar{p}_T - 0.80)}{SE(\bar{p}_T)}$$

Where the formula for the weighted estimate of the proportion is given by the following:

$$\bar{p}_T = \frac{\sum_k W_k p_{Tk}}{\sum_k W_k}$$

And the formula for the weight in site k is given by the following:

$$W_k = \left(\frac{1}{n_k} p_k (1 - p_k) \right)^{-1}$$

And the formula for the standard error is given by the following:

$$SE(\bar{p}_T) = \left(\sum_{k=1}^{m_T} W_{Tk} \right)^{-1/2}$$

If the $z < 1.645$ ($P=0.05$, one-sided), then the null hypothesis will be rejected in favor of the alternative and the primary effectiveness endpoint will be achieved.

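### Section 10.5 can be read as moving both primary tests to the site-weighted z-test when either endpoint differs by site, whereas 10.6.3 and 10.7.3 switch each test only on its own endpoint

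*Combined protocol and SAP*

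**What the plan says.** **Default test.** Section 10.7.1 sets a goal of 80% for Treatment Success at one year and says: "The hypothesis test will be evaluated using the exact binomial distribution as a one-tailed test, using significance level" 0.05. The synopsis and 10.7.3 name the same test.

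**Trigger in 10.5.** Homogeneity across sites is tested for both primary endpoints with the Fisher-Freeman-Halton test. Then: "If the P-value for study site is less than 0.15 for any response, differences between study site will be assumed to exist". In that case an inverse-variance weighted average of site proportions replaces the simple proportion. The section adds: "Both the safety and effectiveness measures will employ weighted proportions as the basis for the statistical test". It refers to 10.6 and 10.7 for how the test is done in that situation. Its last paragraph calls for a Fleiss analysis of effectiveness when the heterogeneity P-value is below 0.15, without saying which endpoint's P-value that is or whether the analysis replaces the exact test.

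**Triggers in the endpoint sections.** For safety, 10.6.3 says: "If there is heterogeneity among the study sites in MAE response, the analysis will be done by the method of Fleiss (1993"). For effectiveness, 10.7.3 says: "If the study site success proportions across study site are not homogeneous, then the method of Fleiss described above will be used". Each looks only at its own endpoint.

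**The concern.** Two homogeneity P-values will exist, one for MAE and one for Treatment Success. If only the MAE value is below 0.15, a literal reading of 10.5 sends Treatment Success to the weighted z-test, while 10.7.3 keeps the exact binomial. Both run at one-sided 0.05, and no sentence says which rule governs.

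Site differences in a 30-day safety composite say nothing about whether one-year success can be pooled. The wider trigger therefore brings no analytic benefit, but it opens a second route to a positive effectiveness result. A primary decision rule should be fixed before either homogeneity P-value is known. At stake is the effectiveness verdict for totals just short of the exact cut-off. The mirror case exists for safety, but it matters less: 10.6.2 expects 16.6% against a goal of 56%, so the choice of test is unlikely to decide the result.

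**Working it through.** **Inputs from the documents.** Goal 0.80, one-sided 0.05 (10.7.1); 132 evaluable subjects and assumed success of 88% (10.7.2); trigger P < 0.15 (10.5); MAE rate 0.166 (10.6.2); at most 30 sites, each capped at 15% of the Pivotal Cohort (5.1), i.e. 0.15 × 150 = 22.5, so 22. Site sizes are not given and are assumed below.

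**1. The plan's own figure.** At n = 132 the exact rule needs at least 114 successes (size 0.0383), with power 76.7% at 88%. The smallest n reaching 80% power is 135, so the stated 132 is reproduced to within 3. Drop-out: 132/0.88 = 150, as stated.

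**2. How often the rules part.** With no true site effect, independent endpoints and each homogeneity test at its nominal 0.15:
- own-endpoint trigger: the effectiveness test switches in 15% of trials;
- any-response trigger: 1 − 0.85² = 27.75%;
- different test chosen: 0.15 × 0.85 = 12.75%, about 13%.

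**3. Exact test at n = 132.** One-sided P at 110, 111, 112, 113 and 114 successes is 0.200, 0.142, 0.097, 0.0625 and 0.038. Everything up to 113 fails.

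**4. Weighted test on the same data.** Section 10.7.3 gives W = n/[p(1−p)] per site, SE = (ΣW)^(−1/2) and z = (weighted p − 0.80)/SE. The printed rule rejects for z < 1.645, the wrong direction for H1: P > 0.80, so rejection is read here as z > 1.645.

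Example with 8 assumed sites, 112/132 in total, homogeneity P about 0.87 (Monte Carlo):

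| Site | 17/20 | 16/19 | 16/18 | 14/17 | 12/16 | 14/15 | 11/14 | 12/13 |
|---|---|---|---|---|---|---|---|---|
| W | 156.9 | 142.9 | 182.2 | 117.0 | 85.3 | 241.1 | 83.2 | 183.1 |

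ΣW = 1191.6 and ΣWp = 1035.3, so weighted p = 0.8688. SE = 1/√1191.6 = 0.0290 and z = 0.0688/0.0290, which is 2.38 before rounding. This passes, while the exact test fails at P = 0.097. The crude rate is 112/132 = 84.8%; the weighted rate is higher because sites nearer 100% get larger weights (14/15 gets 241, 12/16 gets 85).

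**5. Which totals are affected.** This depends on the layout.
- With the same rate at every site, z at 110, 111, 112 and 113 is 1.03, 1.29, 1.55 and 1.83, so only 113 passes.
- With 6 sites of 22: 19,19,18,18,18,18 (110) gives z = 1.11 and fails; 20,20,20,18,17,16 (111, homogeneity P about 0.43) gives 2.28 and passes; 20,20,19,18,18,17 (112) gives 2.13 and passes.
- In simulation of 6 × 22 with all weights defined, totals as low as 104 (78.8%, below the goal) passed in 11% of layouts.

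**6. False-positive rate from trigger scope.** Simulation at true success 0.80, MAE 0.166, independent endpoints, no site effect, and an assumed 0.5 correction for sites at 0% or 100%; 3,000 to 5,000 trials per layout:

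| Assumed layout | Own endpoint | Any response | Excess (points) |
|---|---|---|---|
| 6 × 22 | 12.5% | 14.8% | 2.3 |
| 8 sites | 14.0% | 18.9% | 4.9 |
| 12 × 11 | 15.4% | 21.1% | 5.7 |
| 30 near-equal sites | 4.3% | 4.8% | about 0.5 |
| 30 skewed sites (1–19 subjects) | 9.3% | 10.3% | 1.0 |
| Skewed, sites of ≤4 merged into one | 11.1% | 14.1% | 3.0 |

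The exact test alone gives 3.8%. In both unmerged 30-site layouts every simulated trial had a site at 0% or 100%, where p(1−p) = 0 and the printed weight is undefined. If the analyst then falls back on the exact test, the excess is zero.

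**The case against.** The strongest reply is that 10.5 is loosely worded rather than contradictory. It sets out to test homogeneity for each response and speaks of one overall estimate, so the any-response condition may mean whichever response is in question. It refers to 10.6 and 10.7, where the triggers are endpoint-specific. The Revision 04 change log explains the sentence on both measures as saying that the weighting method is the same for all endpoints, which describes a shared method and not a joint trigger.

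This makes an endpoint-specific intent plausible, and it is why the point is an inconsistency open to two readings and not a certain contradiction. It does not settle the matter. The cross-reference covers how the test is carried out once weighting applies and does not withdraw the trigger just stated. The log gives intent, is not operative text, and does not address the any-response wording.

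A second reply also stands. With up to 30 sites (5.2 mentions 27 US and three European), the average is 132/30 = 4.4 evaluable subjects per site. Layouts of 6 to 12 sites are then more concentrated than the trial may be, and the excess shrinks to about a point or less unless small sites are merged. Section 10.4 provides for merging only in the comparability analysis.

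A reader might go further and infer that no test is named for effectiveness. The documents do not support that: the exact binomial is named in the synopsis, 10.7.1 and 10.7.3. Nor do they support an inference that an analyst would choose between the rules after seeing the data. The text leaves that choice open; it does not show that anyone intends to make it.

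**Conclusion.** The trigger for replacing the exact binomial test is inconsistent between 10.5 and the two endpoint sections, and the last paragraph of 10.5 leaves its P-value unassigned. For effectiveness the readings diverge only when MAE is heterogeneous and Treatment Success is not, about 13% of trials under no site effect; the verdict can then turn on which one is followed.

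The size is uncertain because site sizes are not given. The excess false-positive rate from trigger scope alone runs from about 0 to 6 percentage points: about 2 to 6 with 6 to 12 sites, and smallest with about 30 small sites. It rests on the assumed layouts, independent endpoints, the 0.5 correction and the z > 1.645 reading.

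Two stronger readings should be avoided. The totals 110 to 113 of 132 are not a fixed window: under equal site rates 110 to 112 fail both tests, and under other layouts lower totals pass the weighted one. Nor is the trigger the main source of error inflation. Even with the own-endpoint trigger the simulated rate is 4.3% to 15.4%, against 3.8% for the exact test, and that part comes from the weighted z-test itself.

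**What to change.** - In 10.5, replace the any-response condition and the sentence on both measures with wording that applies each homogeneity result only to its own endpoint.
- In the last paragraph of 10.5, name Treatment Success as the source of the heterogeneity P-value.
- In 10.7.1, state that the exact binomial test decides effectiveness whenever Treatment Success is homogeneous across sites, whatever MAE shows. Put the matching statement for MAE in 10.6.1.

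The cost is a few sentences, with no new data or patients. The downside for the sponsor is that the weighted route to a positive result is available less often. The weighted test's own error rate, its undefined weights at 0% or 100% sites and the printed direction of the z rule need separate correction.

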5. STUDY POPULATION

5.1. PRIMARY INVESTIGATION

Up to 30 sites in the EU, Canada, and the United States will enroll up to 180 subjects including 30 Roll-in subjects and up to 150 patients in the Intention to Treat Pivotal Cohort for endpoint analysis. Total enrollment at a single site is restricted to 15% of the Pivotal Cohort. Following investigator training, each PI will commence patient screening and enrollment under approval per applicable national and local clinical trial requirements* and complete a minimum of one (1) successful Nellix case (Roll-in) in their training phase. This training period may be modified at the discretion of Endologix. Physicians will be directly supervised in each case by designated Endologix staff.

Pivotal Cohort: Up to 150 subjects will be enrolled at a maximum of 30 sites in the US and the EU. This includes the statistically justified sample size of 132 plus an allowance for deviations from assumptions.

Roll-In Cohort: One (1) roll-in subject may be enrolled per site, therefore a maximum of 30 enrolled in the study, to allow for Investigator(s) to receive additional training on the Nellix System. Any roll-in subjects will be screened, consented, treated and followed identically to the main study cohort. However, the roll-in cohort of this study will be evaluated separately.

* Commercially approved clinical trial requirements in the EU (CE Mark), IDE approval in the US, and ITA approval in CA

Confidential. This document and the information contained herein may not be reproduced, used or disclosed without written permission from Endologix, Inc.

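### If the site test gives P<0.15, the deciding effectiveness test is a weighted z-test that almost certainly cannot be computed with about 30 sites, and its rejection rule is printed backwards.

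*Combined protocol and SAP*

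**What the plan says.** Section 10.7.1 names the effectiveness test without condition: "The hypothesis test will be evaluated using the exact binomial distribution as a one-tailed test", at a one-sided 0.05 level, with H0: P ≤ 0.80 and H1: P > 0.80.

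Section 10.5 adds a gate. If the Fisher-Freeman-Halton test across sites gives P<0.15, the overall proportion is "obtained by taking a weighted average of the proportions at each site with the weight being the inverse" of the variance at that site. It continues: "Both the safety and effectiveness measures will employ weighted proportions as the basis for the statistical test". Section 10.7.3 carries this out for effectiveness: "the method of Fleiss described above will be used in the Test arm only to obtain a weighted estimate" of the success proportion. The formulas are

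- W_k = [p_k(1−p_k)/n_k]^−1
- weighted p = ΣW_k p_k / ΣW_k, with SE = (ΣW_k)^−1/2
- z = (weighted p − 0.80)/SE

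The rule printed beneath them is that if z < 1.645, "then the null hypothesis will be rejected in favor of the alternative and the primary effectiveness endpoint will be achieved". Section 10.6.3 uses the same weights for safety, against 0.56.

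On site numbers, section 5.1 says "Up to 150 subjects will be enrolled at a maximum of 30 sites in the US and the EU" and caps any one site at 15% of the Pivotal Cohort. Section 5.2 refers to 27 US and three European sites.

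**The concern.** The weighted z is a decision rule for a primary endpoint, not a sensitivity analysis, and it fails in two ways.

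First, a site where every subject succeeds, or every subject fails, has an estimated variance of zero, so W_k is a division by zero. No section says what to do then. Because 10.7.1 names the exact test unconditionally while 10.5 and 10.7.3 replace it under heterogeneity, the plan also does not say which test decides when the z cannot be computed. At four or five subjects per site and a success rate near 88%, sites at 100% are the norm.

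Second, the printed inequality accepts effectiveness when z is small, against H1.

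At stake is whether the effectiveness verdict is fixed in advance or depends on a repair chosen with the results in view.

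**Working it through.** **The plan's own figure.** Section 10.7.2 gives 132 evaluable subjects for 80% power at a true 88% against 80%, then 132/0.88 = 150. The division is right. The exact one-sided 0.05 test at n=132 needs 114 successes, with type I error 3.8% and power 76.7%. The smallest n with at least 80% exact power is 135, so 132 is close. That small gap is a separate matter.

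**Undefined weights.** Inputs: 132 subjects and 88% (10.7.2), 30 sites (5.1 and 5.2). The documents do not give site sizes. The base case assumes 12 sites of 5 and 18 sites of 4.

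- Chance that a site is at 100%: 0.88^4 = 0.60 for a site of 4; 0.88^5 = 0.53 for a site of 5.
- Expected undefined sites: 18(0.88^4 + 0.12^4) + 12(0.88^5 + 0.12^5) = 17.1, holding about 75 of the 132 subjects.
- Chance that every weight is defined: the product over sites of (1 − 0.88^n_k − 0.12^n_k) = 8.5×10^−12. At a true 80% it is 6×10^−7, with 11.3 undefined sites expected.

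**How often the gate fires.** In 40,000 simulated trials at 88% with identical sites it fired in 5,818 (14.5%). With an assumed between-site SD of 6 points it fired in 28%. All 5,818 gated trials had at least one undefined weight, as did all gated trials in a strongly uneven 30-site layout and in 20 random uneven ones. With fewer sites the share is over 99.9% (12 sites), 99% (10) and 91% (7, the fewest the 15% cap allows).

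**What the repair does: one example.** Same 30-site layout, with failures 3, 2, 1, 1, 1 at five of the sites of 5 and 2, 2, 1, 1, 1, 1 at six of the sites of 4. That is 16 failures, 116/132 = 87.9%, exact P=0.012, site P=0.07, and 30 − 11 = 19 sites at 100%. Here z is read as reject if z > 1.645.

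| Repair | Weighted rate | z | Result |
|---|---|---|---|
| Drop the 19 sites | 69.6% | −1.66 | fails |
| Add 0.5 to successes and failures at every site | 86.0% | 2.32 | passes |
| Add 0.5 only at undefined sites | 87.1% | 2.72 | passes |

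For the first row, ΣW = 252.75, so SE = 252.75^−1/2 = 0.0629 and z = (0.6957 − 0.80)/0.0629. A corrected site uses n_k + 1 in its weight; using n_k instead gives 2.10 and 2.28, which also pass.

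**Across gated trials** at 88% in the base layout, the three repairs reject H0 in 0%, 84% and 95%. They do not all agree in 95% of gated trials (84–98% over the random layouts, 66% in the strongly uneven one). Overall power is 77% for the exact test alone and 66% if undefined sites are dropped (55% at SD 6 points). Type I error over all trials at a homogeneous 80% is 3.2%, 4.3% and 6.5% for the three repairs in the order above, against 3.8% for the exact test alone. In the uneven 30-site layouts the repairs give 2.9–5.9%, 4.7–7.1% and 7.6–9.8%.

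**Direction.** Treat all 132 subjects as one stratum. An observed 70% gives z = −2.51, which the printed rule calls success; 88% gives z = +2.83, which it calls failure. Taken literally, the rule declares effectiveness in 93.7% of trials at a true 80% and in 16.3% at 88%.

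**Safety.** With 30 sites of 5 and the expected 16.6% MAE rate, about 30(0.834^5 + 0.166^5) = 12 sites have no weight. The null of 56% is still rejected in all 40,000 simulated trials under the exact test and under each repair.

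**The case against.** - **The spread between repairs comes mostly from dropping sites.** This stands as a matter of emphasis. The two 0.5 corrections disagree with each other in only about 11% of gated trials, and dropping sites runs against inverse-variance logic, which gives a near-100% site more weight. But the plan rules out none of the three, and dropping strata with undefined estimates is a common software default.
- **Section 10.4 merges small sites.** It says "small sites will be combined into one pseudo-site the size of which will not exceed the size of the largest trial site". That rule is written for comparing sites at baseline, leaves the size threshold open, and forms one pseudo-site only. In the even split, 18 sites of 4 (72 subjects) would have to fit under a cap of 5. In the uneven layout, the merge that was simulated kept the 1-subject and 2-subject sites separate, which guarantees undefined weights. Merging the smallest sites first is the more natural reading, and it still leaves essentially every gated trial undefined.
- **The sign is an obvious misprint.** Probably so: H1, the P-value rule and the one-sided label all point the other way. It still needs correcting, because it is the printed criterion for a primary endpoint.
- **The branch is conditional, and 30 sites is a maximum.** True. But a 0.15 threshold fires in about one trial in seven by chance alone, and even 7 sites leave 91% of gated trials undefined.
- **The cited source may handle zero-variance strata.** This cannot be checked from the documents. The criticism is of the formula and rules as the plan prints them.

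**Conclusion.** The concern holds and must be fixed. Once the site test gives P<0.15, the plan's deciding effectiveness test has, for practical purposes, no computable value at the site number the documents indicate, and no section says what replaces it. This is near-certainty, not logical impossibility. It rests on about 30 sites and on assumed site sizes, but it survived every 30-site layout tried. The printed inequality contradicts H1 whatever the layout. The type I error and power figures for the repairs belong to those repairs, which the plan does not name.

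The safety conclusion is unaffected at the expected event rate. A lesser point applies only with few large sites: where all weights exist, sites near 100% dominate. With seven sites (18, 18, 16, 14, 14 and 12 successes of 19, and 12 of 18), a crude 78.8% becomes a weighted 86.4% with z=2.29. Passing with a crude rate below 80% occurred in 1.2% of all trials with 7 sites at a true 80%, and in none of 40,000 with 30. The documents do not say whether the gate fired.

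**What to change.** Make the exact tests decisive. Suggested text for section 10.5:

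> The exact binomial tests in 10.6.3 and 10.7.3 decide each primary endpoint regardless of the site homogeneity test. If the Fisher-Freeman-Halton P-value is below 0.15, site-level rates and the overall proportion with a site-clustered confidence interval (or a random-intercept logistic model) will be reported as supportive analyses only.

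Remove the W_k, SE and z decision rules from 10.6.3 and 10.7.3. If the sponsor keeps the weighting, the minimum is to state which test decides, fix one rule for sites at 0% or 100%, and correct 10.7.3 to z > 1.645.

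No new data or subjects are needed. The cost is that the deciding test is settled after one-year outcomes exist, since section 8.6 cites 2-year data, and the change should be logged as such. If the gate did fire, report the exact result beside the weighted result under each rule for 0% and 100% sites. The pooled exact test also ignores between-site variance: at an assumed SD of 6 points its type I error is 4.3–5.5% with 30 sites and up to 6.7% with 7. The supportive analysis would show this.
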